2.2. Primary and Secondary Measures and Endpoints

2.2.1. Primary Efficacy Endpoint

There is no primary efficacy endpoint.

2.2.2. Secondary Efficacy Endpoints

There are no secondary efficacy endpoints.

2.2.3. Exploratory Efficacy Endpoints

Exploratory efficacy endpoints are as follows:

- mean change from baseline (28-day run-in period) in the number of migraine days during the 4-week periods after visits 4, 7, and 13
- mean change from baseline (28-day run-in period) in the number of headache days of at least moderate severity during the 4-week periods after visits 4, 7, and 13
- mean change from baseline (28-day run-in period) in the number of migraine days during the 4-week periods after visits 4, 7, and 13 in patients not receiving concomitant migraine preventive medications at baseline
- mean change from baseline (28-day run-in period) in the number of headache days of at least moderate severity during the 4-week periods after visits 4, 7, and 13 in patients not receiving concomitant migraine preventive medications at baseline

- mean change from baseline (28-day run-in period) in the number of migraine days during the 4-week period after the 1st dose of study drug for new patients and placebo-treated rollover patients
- mean change from baseline (28-day run-in period) in the number of headache days of at least moderate severity during the 4-week period after the 1st dose of study drug for new patients and placebo-treated rollover patients
- mean change from baseline (28-day run-in period) in the number of headache days of any severity during the 4-week periods after visits 4, 7, and 13
- mean change from baseline (28-day run-in period) in the number of days of use of any acute headache medications during the 4-week periods after visits 4, 7, and 13
- proportion of patients reaching at least 50%, 75%, and total (100%) reduction in the number of headache days of at least moderate severity during the 4-week periods after visits 4, 7, and 13
- proportion of patients reaching at least 50% and 75% reduction in the number of headache days of at least moderate severity during the 4-week periods after visit 4 who sustain the same level of response during the 4-week periods after visits 7 and 13
- proportion of patients reaching at least 50%, 75%, and total (100%) reduction in the number of migraine days during the 4-week periods after visits 4, 7, and 13
- proportion of patients reaching at least 50% and 75% reduction in the number of migraine days during the 4-week periods after visit 4 who sustain the same level of response during the 4-week periods after visits 7 and 13
- proportion of patients discontinuing concomitant preventive medications during the treatment period
- mean change from baseline (day 0) in disability score in patients with CM, as measured by the HIT-6, at visits 8 and 14
- mean change from baseline (day 0) in disability score in patients with EM, as measured by the MIDAS questionnaire, at visits 8 and 14
- mean change from baseline (day 0) in quality of life, as measured by the MSQOL questionnaire, at visits 8 and 14
- mean change from baseline (day 0) in patient health status, as measured by the EQ-5D-5L questionnaire, at visits 8 and 14
- assessment of patient satisfaction, as measured by the PGIC scale at visits 3, 5, 8, 11, and 14
- mean change from baseline (day 0) in patient depression status, as measured by the PHQ-2 and PHQ-9, at visits 8 and 14
- mean change from baseline (day 0) in patient work productivity and activity impairment, as measured by the WPAI questionnaire, at visits 8 and 14

2.2.4. Safety and Tolerability Endpoints

The safety and tolerability endpoints for this study are as follows:

- occurrence of adverse events throughout the study
- changes from baseline in clinical laboratory (serum chemistry, hematology, coagulation, and urinalysis) test results
- abnormal standard 12-lead electrocardiogram (ECG) findings
- changes from baseline in vital signs (pulse, systolic and diastolic blood pressure, body temperature, and respiratory rate) measurements
- abnormal physical examination findings
- abnormal local injection site tolerability findings (ie, erythema, induration, and ecchymosis) and occurrence of injection site pain
- suicidal ideation and behavior as suggested by the electronic Columbia-Suicide Severity Rating Scale (eC-SSRS)

2.2.5. Pharmacokinetic/Immunogenicity/Biomarker Endpoints

2.2.5.1. Pharmacokinetic Endpoints

There are no prespecified pharmacokinetic endpoints.

2.2.5.2. Immunogenicity Endpoint

The immunogenicity endpoint is the incidence and impact of ADAs on clinical outcome after monthly sc doses of TEV-48125 and at 7.5 months after stopping treatment.

2.2.5.3. Biomarker Endpoints

The biomarker assessments and endpoints will be provided in a separate document by Personal Medicine and Pharmacogenomics.

2.3. Sample Size and Power Considerations

There are no statistical considerations for this sample size. A total of 1842 patients (867 patients from Study TV48125-CNS-30049, 675 patients from Study TV48125-30050, and approximately 300 patients who did not participate in the pivotal efficacy studies) are planned for enrollment, and a 30% drop-out rate is anticipated.

2.4. Randomization and Blinding

2.4.1. Randomization

This is a randomized study with patients being stratified by gender, country, and preventive medication use at baseline (yes, no) during the pivotal efficacy studies or during this study if they are not rolling over from the pivotal efficacy study.

Patients rolling over from the pivotal efficacy studies who were randomized to the active treatment groups will continue receiving the same treatment throughout the study. Patients rolling over from the pivotal efficacy studies who received placebo and new patients will be randomly assigned in a 1:1 ratio to receive quarterly TEV-48125 at 675 mg or monthly TEV-48125 at 225 mg (Note: Patients with CM will receive a 675-mg loading dosing at visit 2 and TEV-48125 at 225 mg at each subsequent visit.).

Patient randomization codes will be maintained in a secure location within Teva Clinical Supply Chain. At the time of analysis, when treatment codes are needed, the Teva statistician assigned to the study will make a request to unblind and will receive the unblinded codes.

2.4.2. Blinding/Unblinding

In order to blind the treatment groups based on both dose-volume and number of injections, each patient will receive three 1.5 mL sc injections (three 1.5 mL sc injections of active drug, one 1.5 mL sc injection of active drug and two 1.5 mL injections of placebo, or three 1.5 mL injections of placebo) at visits 2, 5, 8, and 11 and 1 injection at all other visits as detailed in the [Table 1](#) and [Table 2](#).

The sponsor, investigators, study staff (except for staff involved in bioanalytical analyses), and patients will be blinded to treatment assignment. The Sponsor will be unblinded when the pivotal efficacy studies have been unblinded. A computer-generated master randomization list will be provided to drug packaging facilities. Packaging vendor(s) will prepare study drug into kits according to Good Manufacturing Practice procedures. Kits will be identical in appearance, and will contain 1 prefilled syringe with active drug or placebo. Adequate kit supply for upcoming study visits will be managed by interactive response technology (IRT) and kept (refrigerated at 2°C to 8°C) on site.

For information about personnel who may be aware of treatment assignments, see protocol Section 3.7. These individuals will not be involved in conduct of any study procedures or assessment of any adverse events.

In case of a serious adverse event or pregnancy, or in cases when knowledge of the study drug assignment is needed to make treatment decisions, the investigator may unblind the patient's drug assignment as deemed necessary, mainly in emergency situations. Individual treatment codes, indicating the treatment randomization for each randomized patient, will be available to the investigator(s) and/or pharmacist(s) at the study center via the IRT, both via telephone and internet. If possible, the sponsor should be notified of the event prior to breaking of the code. If this is not possible, the sponsor should be notified immediately afterwards, and the patient's drug code assignment should not be revealed. Breaking of the treatment code can always be performed by the site without prior approval by the sponsor.

When a blind is broken, the patient will be withdrawn from the study, and the event will be recorded onto the CRF. The circumstances leading to the breaking of the code should be fully documented in the investigator's study files and in the patient's source documentation. Treatment assignment should not be recorded in any study documents or source documents.

In blinded studies, for adverse events that are defined as suspected unexpected serious adverse reaction (SUSAR) (ie, reasonable possibility; see protocol Section 7.1.4), Global Patient Safety & Pharmacovigilance may independently request that the treatment code be revealed (on a case-

by-case basis) to comply with regulatory requirements. The report will be provided in an unblinded manner for regulatory submission. If this occurs, blinding will be maintained for the investigator and for other personnel involved in the conduct, analysis, and reporting of the data.

2.5. Sequence of Planned Analyses

2.5.1. Interim Analyses

In support of a biologics license application (BLA), a cut-off date will be determined for this study and all data accumulated up to the cut-off date will be analyzed. An interim CSR will be prepared on the interim data.

2.5.2. Final Analyses and Reporting

All final, planned analyses identified in this SAP will be performed after the database lock.

3. POPULATIONS /ANALYSIS SETS

3.1. Intent to Treat Population

The intent-to-treat (ITT) population will include all patients who are randomized in this study for long-term safety evaluation, regardless if they receive study treatment or not. In this population, treatment will be assigned based on the treatment to which patients are randomized (see Section 2.4.1 for the details of the patients randomization), regardless of which treatment they actually received.

3.2. Safety Population

The safety population will include all patients who receive at least 1 dose of TEV-48125 in this study. In this population, treatment will be assigned based upon the treatment patients actually receive, regardless of the treatment to which they are randomized.

3.3. Full Analysis Set

The full analysis set (FAS) will include all patients in the safety population and have at least 10 days of efficacy assessments by e-diary post the 1st injection for this study.

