9.2.3. Full Analysis Set

The full analysis set (FAS) will include all patients in the safety analysis set and have at least 1 postbaseline efficacy assessment.

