4.5. Handling Withdrawals and Missing Data

A patient's monthly number of days/hours of efficacy variables during the 4-week period after each dose of study drug will be calculated for months 1, 2, 3, 6 and 12. If a patient has missing diary days when calculating the monthly variables, the following method will be used to handle the missing data.

- If a patient has ≥ 10 days of e-diary data for a month, the monthly number of days/hours of efficacy variables will be prorated to 28 days for that month.
- If a patient has < 10 days of e-diary data for a month, the monthly number of days/hours of efficacy variables will be considered as missing for that month.

The missing questionnaire items handling for the MSQOL questionnaire ([Appendix E](#)) is discussed in [Appendix F](#): scoring instruction for MSQOL.

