6. EFFICACY ANALYSIS

6.1. General

The FAS will be used for all efficacy analyses. The patients with CM and patients with EM will be summarized separately for their efficacy endpoints. The descriptive statistics will be presented by treatment group and visits/months for new patients and placebo-treated rollover patients, TEV-48125-treated rollover patients, and overall under the same treatment, unless otherwise specified.

Efficacy endpoints will be derived from headache related question responses (eg, occurrence of headache, duration of headache in each day, maximum severity of headache, and acute migraine-specific medication use etc. [Appendix A](#)) collected daily using an electronic headache diary device for month 1, 2, 3, 6 and 12.

Following the Classification Committee of the International Headache Society guidelines ([Silberstein et al 2008](#)), headache days of at least moderate severity for both CM and EM patients will be defined for the purpose of this study as a calendar day (0:00 to 23:59) when the patient reports:

- a day with headache pain that lasts ≥ 4 hours with a peak severity of at least moderate severity
- or
- a day when the patient used an acute migraine-specific medication (triptans or ergots) to treat a headache of any severity or duration

Migraine day is endorsed based on the same criteria as described in the pivotal studies. For CM patients, a migraine day is endorsed when at least 1 of the following situations occur:

- a calendar day (0:00 to 23:59) demonstrating ≥ 4 consecutive hours of a headache meeting criteria for migraine with or without aura
- a calendar day (0:00 to 23:59) demonstrating ≥ 4 consecutive hours of a headache meeting criteria for probable migraine, a migraine subtype where only 1 migraine criterion is missing
- a calendar day (0:00 to 23:59) demonstrating a headache of any duration that was treated with migraine-specific medications (triptans and ergot compounds)

For EM patients, a migraine day is endorsed when at least 1 of the following situations occur:

- a calendar day (0:00 to 23:59) demonstrating ≥ 2 consecutive hours of a headache meeting criteria for migraine with or without aura
- a calendar day (0:00 to 23:59) demonstrating ≥ 2 consecutive hours of a headache meeting criteria for probable migraine, a migraine subtype where only 1 migraine criterion is missing

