6.4.1. Variable Definition

6.4.1.1. Headache Diary Data

The exploratory efficacy variables derived from the headache e-diary data include mean change from baseline in the monthly average number of migraine days, headache days of at least moderate severity, headache days of any severity, days of use of any acute headache medications, headache hours of at least moderate severity, headache hours of any severity, days with nausea or vomiting, days with photophobia and phonophobia *during the 4-week periods* after visits 2, 3, 4, 7, and 13 for months 1, 2, 3, 6, and 12. The change from baseline is calculated as *postbaseline value – baseline value*, where the postbaseline values are derived using formula (1) in Section 6.1 and the baseline values are carried forward from the pivotal studies or calculated using formula (2) in Section 6.1 for new patients

If a patient has missing days of entries in the e-diary for a month, his/her monthly average number of days of study variables *during the 4-week period* for that month will be handled as discussed in Section 4.5.

The percent reduction in the monthly average number of migraine days *during the 4-week period* after each dose at visits 2, 3, 4, 7, and 13 for months 1, 2, 3, 6, and 12 will be calculated by formula (3) in Section 6.1. The patient is considered as a responder reaching 50%, 75%, or 100% reduction if his/her percent reduction is 50% or more, 75% or more, or 100%, respectively. Similar definition will be applied to calculate the proportion of patients reaching at least 50%, 75%, or 100% reduction in the monthly average number of headache days of at least moderate severity during the 4-week period for months 1, 2, 3, 6 and 12. If a patient is early discontinued from the study, he/she will be counted as a non-responder.

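### Treated patients who leave the study before 10 diary days fall outside the FAS and so escape the SAP's non-responder rule, which biases responder rates slightly upward

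*SAP*

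**What the plan says.** SAP section 3.2 defines the treated patients: "The safety population will include all patients who receive at least 1 dose of TEV-48125 in this study". Section 3.3 narrows this for efficacy: "The full analysis set (FAS) will include all patients in the safety population and have at least 10 days of efficacy assessments by e-diary", counted from the first injection in this study. The 10 days are a running total and not a monthly requirement. Section 6.1 then states "The FAS will be used for all efficacy analyses", and section 5.1 repeats it. Neither makes an exception for responder or questionnaire endpoints.

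On responders, section 6.4.1.1 says: "If a patient is early discontinued from the study, he/she will be counted as a non-responder". Neither 6.4.1.1 nor 6.4.2.1 names a denominator other than the FAS. Section 4.5 has a separate monthly rule: with fewer than 10 diary days in a month, "the monthly number of days/hours of efficacy variables will be considered as missing for that month".

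Protocol section 9.2.3 had a looser entry condition, "all patients in the safety analysis set and have at least 1 postbaseline efficacy assessment", which a single questionnaire would meet. The SAP amendment history attributes the 10-day condition to FDA review comments. SAP section 13, which is for changes to protocol-specified analyses, records none.

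**The concern.** The non-responder rule exists so that patients who give up on treatment are not lost from the responder tables. Because the FAS is fixed first, and fixed on diary use after dosing, the patients who give up soonest are removed before the rule can reach them. They are in neither numerator nor denominator. Every one of them would have been scored a failure, so the error has one direction.

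The responder tables show new and placebo-treated rollover patients beside patients who already completed a pivotal study on active drug. Early loss might differ between these columns, although the documents give no figures. The results also feed an interim report in support of a licence application (SAP section 2.5.1).

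A lesser issue is that HIT-6, MIDAS, MSQOL, EQ-5D-5L, PGIC, PHQ, WPAI and preventive-medication discontinuation are not diary measures, yet a diary condition decides who enters their summaries.

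**Working it through.** **The plan's own figure.** SAP section 2.3 gives 867 + 675 + about 300 = 1842 patients and anticipates 30% drop-out. The sum reproduces. There is no power or alpha to reproduce, because no inferential analysis is planned (SAP section 4.4).

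**Who is affected.** With daily entry, a patient who leaves before about day 10 cannot reach 10 diary days. The documents do not say when drop-out occurs, so the share q leaving that early is an assumption. I take all 1842 as treated and place the 30% within the 336-day treatment period:

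- Uniform timing: q = 0.30 × 10/336 = 0.89%; 1842 × 0.0089 ≈ 16 patients.
- Constant hazard: h = −ln(0.7)/336; q = 1 − exp(−10h) = 1.06%; 1842 × 0.0106 ≈ 19 patients.
- Constant hazard over 533 days, to the final visit: q = 0.67%, about 12 patients.
- A wider case: if everyone leaving in the first 28 days had so patchy a diary as to miss the threshold, constant hazard over 336 days gives q = 2.9%, about 54 patients.

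**Effect on a responder rate.** Let r be the rate with all treated patients in the denominator. If a share q, all non-responders, is dropped, the reported rate is r/(1 − q).

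| Share dropped, q | Patients | r = 30% | r = 50% | r = 60% |
|---|---|---|---|---|
| 1.06% | 19 | +0.3 | +0.5 | +0.6 |
| 2% | 37 | +0.6 | +1.0 | +1.2 |
| 3% | 55 | +0.9 | +1.5 | +1.9 |
| 5% | 92 | +1.6 | +2.6 | +3.2 |

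Entries are percentage points. The 5% row needs 5/30, or one sixth, of all drop-out to fall in roughly the first 10 days.

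**Patients who stay.** Diary data are analysed for months 1, 2, 3, 6 and 12, so 5 × 28 = 140 days are scheduled and the threshold is 10/140 = 7% of them. Treating entries as independent, a patient completing 20% of days misses the threshold with probability about 0.0006% over 140 days, and 1.8% over the first 84. At 10% completion the figures are 9.7% and 67%. Apart from early leavers, only patients who hardly use the diary are excluded.

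**The case against.** The strongest reply is that nothing here conflicts. Section 6.1 sets the population, section 6.4.1.1 scores discontinuers within it, and the threshold followed FDA comments. That stands. A reader might infer that the two SAP rules cannot both be carried out. They can, but the order in which they apply means the earliest failures are not scored. The FDA comments are not reproduced, and nothing in the documents shows that the threshold was meant to override the non-responder rule or to govern non-diary measures. The SAP preface lets the SAP prevail over the protocol, with discrepancies explained in the study report, so the difference from protocol 9.2.3 is a matter of recording.

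A reader might also score every treated patient with fewer than 10 diary days as a failure and discount the reported rate accordingly. The SAP does not support this: section 6.4.1.1 makes only discontinued patients non-responders, and a retained patient with too few entries has a missing month under section 4.5.

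A third tempting reading is that many valid visit 8 and visit 14 questionnaires are thrown away. That is very unlikely, given the 7% threshold and the entry requirements (24 of 28 run-in days for new patients; at least 75% in the last pivotal month for rollovers). Very early leavers may complete questionnaires at the early withdrawal visit. For them, MIDAS (3-month recall) and MSQOL (4-week recall) would largely describe the time before the first dose in this study.

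Finally, the stakes are limited. Efficacy is exploratory and descriptive, and SAP section 5.2 reports both the safety-population and FAS counts. Those counts let a reader bound the loss, but they do not separate early leavers from retained patients with little diary data.

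**Conclusion.** The point holds in a limited form. The direction is certain: removing patients whom the SAP would have scored as non-responders can only raise responder rates. For sustained response the same is true if the denominator is the FAS, which is the only one the SAP provides. If those rows were instead conditional on month 3 response, early leavers would not enter either way.

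The size is small: about 1% of treated patients and about 0.5 points at a 50% rate, assuming that the stated 30% drop-out is spread evenly over 336 days and that all planned patients are treated. Larger effects need front-loaded drop-out or patchy diaries among first-month leavers. The documents support neither, and the completed pivotal study required of rollovers makes heavy early loss less likely.

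The diary condition on questionnaires and preventive discontinuation is unnecessary, but removing it would change little numerically. The primary safety analyses use the safety population and are untouched.

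**What to change.** - **Diary mean changes:** keep the 10-day FAS.
- **Responder and sustained-response rows:** state the denominator as the FAS plus all treated patients who discontinued the study before reaching 10 diary days, with the latter counted as non-responders.
- **Patients who remain in the study with fewer than 10 diary days:** leave them as missing under SAP section 4.5 and report their number by treatment group.
- **Questionnaire change scores:** summarise treated patients with a baseline and at least one post-baseline value of that measure.
- **PGIC:** summarise treated patients with at least one post-baseline value, since PGIC has no baseline.
- **Preventive-medication discontinuation:** summarise treated patients who used a preventive at baseline.
- **SAP section 13:** record the departure from protocol section 9.2.3 and the reason for it.

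The cost is a few sentences in the SAP, a second n to footnote in the responder tables, and slightly lower responder rates. No additional data are needed.
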